### **Measures**

**Baseline Screening** As part of the CNRA general evaluation protocol (HSC-MS-05-0322), to determine eligibility, participants will receive a comprehensive medical and psychiatric evaluation including: a medical-history questionnaire, physical examination, laboratory chemistries (e.g., blood chemistry screen, complete blood count, urinalysis and urine pregnancy test), and ECG. Clinicians will conduct the **SCID**, the **ASI**, the **KMSK** assessment of lifetime substance use interview, and **TLFB**.

**Smoking-Related Measures** Nicotine dependence will be assessed using the **FTND**. Self-report will be used to collect self-reported number of cigarettes used in the past 7 days. Nicotine craving will be assessed using a brief, 10-item version of the **Questionnaire of Smoking Urges (QSU-brief)**. Nicotine withdrawal will be assessed using the 8-item **MNWQ**. **Breath CO** will be used to measure severity of smoking and overnight smoking abstinence.

**Sleep-Related Measures** Quality of sleep in the past week will be primarily assessed using the **PROMIS Sleep Disturbance Short Form**, a well validated and reliable subjective measure of sleep quality. Secondary measures will include the **Epworth Sleepiness Scale**, and **PSQI**. Sleep actigraphy (total hours, levels, and movement) will be measured via the Garmin Vivosmart® 3 device as validated by recent research.

**Stress and Anxiety Measures** Stress and anxiety will be assessed using standard, validated questionnaires using the **HAM-A**, **PSS**, and **DASS-21**. Additionally, a single-item **VAS** measure will be used to assess self-reported stress.

**Human Laboratory Measures** Experimental measures will be conducted on study days 1 and 8. Participants will be instructed to stop smoking by 10 pm the day before, in order to ensure they meet the breath CO criterion ( $CO \leq 4$  ppm) indicating overnight abstinence. In addition to measuring nicotine craving and withdrawal using the QSU and MNWQ, respectively, we will conduct two additional assessments.

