## DATA SAFETY MONITORING PLAN

### **E1. Human Subjects Involvement and Participant Characteristics**

The study will test 20 current cigarette smokers, 18 to 65 years old that report smoking at least 10 cigarettes/day (half pack). Notably, because the study medication (suvorexant) is contraindicated with alcohol use, we will exclude subjects with alcohol use disorders (via screening at intake). We will also exclude those individuals meet DSM-5 criteria for an alcohol use disorder or report recent problem drinking (5/4 drinks for males/females in < 2.5 hours or > 10 alcoholic drinks per week) or those who report being unwilling to stop using alcohol in the evening for the two weeks of the study. Additional exclusion criteria include individuals that are pregnant, nursing, or planning on becoming pregnant during the course of the study; or if they have any other illness, condition, or use of medications which in the opinion of the PI and/or admitting physician would preclude safe and/or successful completion of the study. This will be accomplished via full medical evaluation at intake by [name], M.D., CNRA Medical Director. The study will be conducted at the Neurobehavioral Research Laboratory at the CNRA. Recruitment strategies will include local advertising in print media, public service announcements on radio, and referrals to CNRA in the Houston metropolitan area. We expect to enroll a minimum of 2 participants per month to meet recruitment goals; however, we will be able to accommodate four simultaneous participants. Participants will be required to participate for 3 days (intake/screening, baseline observations, and one follow-up observation one week later). Research data will be collected at each scheduled time point.

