## **E3. Potential Risks**

**Suvorexant** (BELSOMRA) is an orexin receptor antagonist indicated for the treatment of insomnia, characterized by difficulties with sleep onset and sleep maintenance. Recommended dose is 10 mg, 1x per night taken within 30 minutes of going to bed, with at least 7 hours of planned time before awakening. If the 10 mg dose is well tolerated but not optimally effective, it can be increased but not to exceed 20 mg once daily. Medication is taken PO, with dosage in tablets of 5, 10, 15, and 20 mg. Contraindicated in patients with narcolepsy. Precautions include daytime somnolence; dose-related risk of impaired alertness and motor coordination, including impaired driving; patients taking 20 mg should be cautioned against next-day driving; nighttime “sleep-driving” and other complex behaviors while out of bed and/or not fully awake; worsening of depression or suicidal thinking; compromised respiratory function; sleep paralysis, hypnagogic/hypnopompic hallucinations. Risk of the above symptoms increases with use of CNS depressants and alcohol. In obese women (BMI > 30), there is increased risk of exposure-related adverse effects. Belsomra is a schedule-IV compound with mild/modest abuse-potential in the same class as existing sleep medications and anxiolytics. The most common adverse reactions include somnolence and slowed motor coordination. Not recommended for use in patients taking strong CYP3A inhibitors, efficacy may be reduced, or for patients with severe hepatic impairment. Based on animal data, Belsomra may cause fetal harm.

**Risks for Behavioral and Psychometric Testing.** Items on certain psychological/psychiatric questionnaires and interviews might be perceived as personally discomforting to some subjects. Similarly, subjects may experience discomfort due to withdrawal symptoms as part of the smoking relapse assessment. With regard to the actigraphy sleep monitoring, participants may experience mild discomfort while acclimating to wearing the device during sleep. While subjects may be uncomfortable reporting these issues, the risks of serious sequelae are extremely low.

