**Other Protections Against Risk.** The following procedures will be taken to safeguard against adverse medication events: (1) careful initial intake evaluation to determine eligibility based on inclusion/exclusion criteria; (2) thorough physical evaluation prior to treatment, consisting of physical examination, standard laboratory tests, electrocardiogram, toxicology screen, pregnancy test, and vital signs; (3) repeated tests during treatment; (4) daily monitoring of pill taking using MEMS caps, returned pill counts, and self-report; (5) weekly review of adverse events and medication compliance; (6) regular evaluation by the study physician ([name]). Specific criteria will be used to exclude potential subjects for whom any of the study medications is contraindicated. Any abnormal physiological, psychological, or behavioral event will be evaluated and, if indicated, will result in the subject's removal from the study.

For all three experiments included in this project, we will use an Adverse Event Log (AEL) based on NIDA SAFTEE procedures. The AEL will record the duration, severity, and frequency of any adverse events, signs, and symptoms. An evaluation will be made as to the event's relationship to the study drug(s), scaled as unrelated, unlikely, possible, and probable. The AEL will be included in 1   IRB APPROVAL DATE: 10/12/2023

Subjects will be monitored regularly for compliance with the study requirements, including the dosing regimen and breath alcohol testing upon arrival at the laboratory each day of testing. Written and verbal information about the medication will be given to all participants. This information will remind the subject to: (1) take food shortly after medication if needed to relieve gastric irritation; (2) inform the treatment research clinic nurse or physician of any over-the-counter and prescription medication taken, especially: cough medication, diarrhea medication, narcotic medication; (2) notify treatment research clinic nurse or physician of any side effects that persist or worsen. The study physician, nurse, and PI will review cases involving clinical deterioration of increased symptomatology or substance abuse. Appropriate actions will be taken, including study termination with proper referral.

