#### **E9. Data and Safety Monitoring Plan (NIH/NIDA specific issues)**

1. The Principal Investigator will be responsible for knowing the policies of the local IRB (the UT – Houston Committee for the Protection of Human Subjects, CPHS). The PI will adhere to CPHS policies and maintain accurate documentation of CPHS correspondence and reports (e.g., annual report). The PI is responsible for documentation and handling of all possible study-related adverse events. The Treatment Research Clinic (TRC) within our Center for Neurobehavioral Research on Addictions (CNRA) has longstanding data collection and safety monitoring systems in place that will be available for the proposed study. These include staff training, weekly audit of data collection/entry, medical screening with results reviewed by on-site nurse and physician, use of standardized assessments, continued medical monitoring during the study, procedures to monitor medication compliance (MEMS caps, texts). As PI, [name] will assure that the above systems are in place and functioning properly during the study.

2. A Monitoring Committee will provide additional, independent oversight of data related to subject safety. This committee will perform the following activities: (a) review the research protocol and plans for data and safety monitoring; (b) evaluate study progress, including data quality, participant recruitment rates, retention rates, outcome and adverse experience data, and risk versus benefit profile; (c) make recommendations to the PI for a discontinuation of study medication for an individual patient based on adverse experiences; (d) make recommendations to terminate the study because of safety concerns; and (e) protect the confidentiality of the data and the results of monitoring. The Committee will be blind to study medication, unless they believe that termination of the trial is warranted. This committee meets annually to review all CNRA studies, and this present study will be added to the DSMB review in 2020. The DSMB report is submitted annually to CPHS.

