The following procedures will be taken to safeguard against adverse medication events: (1) careful initial intake evaluation to determine eligibility based on inclusion/exclusion criteria (including exclusion for alcohol use disorder or frequent regular use); (2) thorough physical evaluation prior to treatment, consisting of physical examination, standard laboratory tests, electrocardiogram, toxicology screen, pregnancy test and vital signs; (3) repeated tests during treatment; (4) daily monitoring of pill taking using MEMS caps, returned pill counts, and self-report; (5) weekly review of adverse events and medication compliance; (6) evaluation by the study physician ([name]). Specific criteria will be used to exclude potential subjects for whom any of the study medications is contraindicated. Any abnormal physiological, psychological, or behavioral event will be evaluated and, if indicated, will result in the subject's removal from the study.

For this project, we will use an Adverse Event Log (AEL) based on NIDA SAFTEE procedures. The AEL will record the duration, severity, and frequency of any adverse events, signs, and symptoms. An evaluation will be made as to the event's relationship to the study drug, scaled as unrelated, unlikely, possible, and probable. The AEL will be included in the report to DSMB. Relevant information is also included in section E9.

**Referral to Treatment.** As noted above, at study end subjects will receive a follow up medical examination and a session with a masters-level licensed counselor or RN in our treatment research clinic, who will provide information about treatment options and referrals. If depression or suicidal ideation is measured at risk during the study, participation will be terminated and appropriate referrals made (see above).

**Incomplete Disclosure.** We have no elements of deception in this project, other than withholding of dose information to subjects about dose contents on days of testing (e.g., suvorexant or placebo). However, informed consent documents will contain full disclosure of the drug that may be received during the course of the experiments, along with potential side effects. No information about study risks will be withheld from subjects.

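### An adverse-event stop is written as study exit and no visible text keeps Day 8 after a medication stop, so a mid-week event can cost the only post-treatment laboratory observation (low importance)

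*Combined protocol and SAP*

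**What the plan says.** The adverse-event rule in E4 (Other Protections Against Risk) reads "Any abnormal physiological, psychological, or behavioral event will be evaluated and, if indicated, will result in the subject's removal from the study". E10 (Safety of Research Participants Outside of the Research Site) repeats it: an abnormal event "will be evaluated and, if indicated, will result in the subject's removal from the study". Both depend on clinical judgement, but the outcome they name is exit from the study.

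The only visible mention of a medication-only stop is E9, item 2(c), where the Monitoring Committee may "make recommendations to the PI for a discontinuation of study medication for an individual patient based on adverse experiences". It is silent on later visits, and the committee meets once a year against a 7-day course.

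On timing, Human Laboratory Measures states "Experimental measures will be conducted on study days 1 and 8", and E1 lists attendance as "intake/screening, baseline observations, and one follow-up observation one week later". Table 1 shows no visit between Day 1 and Day 8. During that week, E4 asks participants to "notify treatment research clinic nurse or physician of any side effects that persist or worsen".

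Missingness & Multiple Comparisons plans maximum likelihood, imputation, pattern-mixture models and sensitivity analyses. It covers how absent values are analysed, not whether Day 8 is still collected after a stop. E10 plans a closing medical examination and counsellor session for all subjects, but lists no trial outcomes there.

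**The concern.** A participant removed mid-week has no Day 8 QSU, heart rate, cortisol, latency or PROMIS value. If removal depends only on Day 1 data, the planned mixed model copes. If it depends on how the person was doing near Day 8, and happens more in one arm, the time-by-group estimate is biased. With one post-treatment visit, a pattern-mixture model can explore this only through assumptions that the data cannot test.

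Unequal removal is plausible. E3 says "The most common adverse reactions include somnolence and slowed motor coordination", so reports could be more frequent on active drug and linked to the sleep outcomes of Hypothesis 2. The direction is not fixed: losing people whose craving or stress worsened would favour suvorexant, while losing people who slept more could count against it on sleep.

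**Working it through.** **From the documents:** 10 per arm, alpha 0.05, 80% power, f = 0.66 and a posterior threshold of 0.75 (Sample Size and Power Considerations); time-by-group interaction with a random intercept (Specific Analyses).

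**Assumed, because the documents give no figures:** SD 1 at each visit; Day 1 to Day 8 correlation ρ = 0.3, 0.5 or 0.7; k losses, active arm only; removal reason correlated r = 0.5 with a worse Day 8 score; stop risk p = 2%, 5% or 10%.

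1. *The plan's figure.* Noncentral F with df (1, 18) and λ = f²N gives 80% power at f = 0.662, and 79.7% power at f = 0.66. The stated value reproduces as a two-group comparison with all 20 complete. With λ = (2f)²n₁n₂/N, the detectable f is 0.683 after one loss (10 v 9) and 0.708 after two (10 v 8). Lost power is a minor issue.

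2. *Chance of at least one active-arm loss.* 1 − (1 − p)¹⁰ = 18%, 40% and 65%.

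3. *Standard error with no loss.* Each change score has variance 2(1 − ρ), so SE = √(2 × 2(1 − ρ)/10) = √(0.4(1 − ρ)).

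4. *Selection bias.* The two largest expected normal order statistics of 10 are 1.539 and 1.001. Losing the top k shifts the mean removal score of those left by c₁ = 1.539/9 = 0.171 or c₂ = 2.540/8 = 0.3175. Because the model borrows from Day 1, bias = r(1 − ρ²)cₖ.

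| | ρ = 0.3 | ρ = 0.5 | ρ = 0.7 |
|---|---|---|---|
| SE, no loss | 0.53 | 0.45 | 0.35 |
| Bias, one lost | 0.078 | 0.064 | 0.044 |
| Bias, two lost | 0.144 | 0.119 | 0.081 |

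   Simulation (20,000 trials per setting, random-intercept-equivalent model, near-flat prior) agrees: 0.04 to 0.08 SD for one loss and 0.08 to 0.15 for two. If loss depends on Day 1 only, bias is within 0.01.

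5. *False signals.* With no true effect and no loss, 25% of trials reach a 0.75 posterior probability of benefit on one outcome. With one selective loss the simulated share is 29–31%, and with two 32–36%. With r = −0.5 it falls to 20–21% and 16–19%.

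6. *Weighted by stop risk.* At p = 2%, 5% and 10%, average bias is about 0.01, 0.02–0.04 and 0.04–0.07 SD. The false-signal share is 25–26%, 27% and 29–30%.

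7. *What keeping Day 8 costs.* If a stopped person has lost the drug effect, k such people among 10 understate a true effect δ by δk/10. For one person that is 0.05 SD at δ = 0.5, 0.10 at δ = 1, and 0.13 at δ = 2 × 0.66 = 1.32 (read in Day 8 SD units). Dilution equals the one-loss bias at δ = 0.044/0.1 = 0.44 to 0.078/0.1 = 0.78. Below that range keeping the value gives the smaller bias; above it, dropping does. Root mean squared error for the on-drug effect, from simulation across ρ:

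| True effect | One person: kept v lost | Two people: kept v lost |
|---|---|---|
| 0.5 SD | 0.35–0.53 v 0.36–0.55 | 0.36–0.54 v 0.37–0.57 |
| 1 SD | 0.36–0.54 v 0.36–0.54 | 0.40–0.57 v 0.37–0.57 |
| 1.32 SD | 0.37–0.54 v 0.36–0.54 | 0.43–0.59 v 0.37–0.56 |

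**The case against.** The strongest objection is that keeping Day 8 does not help at the effect size in the plan's own power statement. At 1 to 1.32 SD, off-drug values bias the on-drug estimate more than selective loss does, and root mean squared error is no better or worse. The stated goal is mechanistic, the half-life is about 12 hours, and PROMIS covers the past week, so a kept PROMIS score mixes on-drug and off-drug nights. All of this stands. A reader might infer that an observed Day 8 value removes the need for assumptions at no cost. It does not: it changes what is being estimated, and an analysis without the off-drug values brings the missing-data assumption back.

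The second objection is that the route is speculative. Removal applies only if indicated, E9 recognises a medication-only stop, and where E4 and E10 describe sedation at visits the response is to keep the person on site and arrange a taxi. Actigraphy recorded before a stop may survive for sleep duration and restlessness. This also stands, and it limits the point to what can happen. A reader might infer that any adverse event forces removal and Day 8 will be lost; the conditional wording does not support that.

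The third objection is that missing data are already planned for. That is true of the analysis, and it would be wrong to say that the plan ignores informative loss. But those methods do not recover an observation that was never taken.

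**Conclusion.** The gap is real and of low importance. The two statements of the rule make study exit the named result of an indicated event, Day 8 is the only laboratory observation after dosing, and nothing visible preserves it. The consent pages are not available and may address the point. The sizes above rest on assumed correlations, on losses confined to the active arm and on assumed stop risks; the documents supply none of these. On those terms the average bias is a small fraction of the standard error, in a trial that calls itself exploratory.

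Two further inferences are not supported. One is that results would necessarily favour suvorexant: the sign depends on why people are removed. The other is that the suicidality rules in E4 and E10 share the fault. The CSSRS is given at visits, before the first dose or after the last, so those rules are not a route to this mid-week loss.

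**What to change.** In both statements of the rule, write stopping study medication and leaving the study as separate steps, consistent with E9 item 2(c). Unless consent is withdrawn or the study physician objects, keep Day 8 after a medication stop with QSU, MNWQ, breath CO, PROMIS and VAS, under the same abstinence rule ("Participants will be instructed to stop smoking by 10 pm the day before"). Retain actigraphy from before and after the stop. Do the cold-pressor and smoking tasks only with physician agreement. Leave the suicidality removal rules unchanged, and leave the decision on which events stop medication or participation to the clinicians.

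Flag off-drug values. Report the time-by-group contrast with them (by randomised group) and without them, and name the primary one beforehand.

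The cost is protocol wording plus a $55 visit ($50 attendance, $5 travel), already inside the stated $234 (40 + 2 × 50 + 50 + 2 × 5 + 34). The closing medical examination could share the day. Heart rate, cortisol and latency may still be missing, so the dependable gain is mainly in the questionnaires, with PROMIS read as a mixed week.

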#### **E5. Potential Benefits of the Proposed Research to the Subject and Others**

All services provided in these studies will be free. The studies should help compliment and advise clinical research focused on stopping cigarette smoking and preventing relapse. Subjects will be told if unusual information is discovered during the study that will make a difference in treatment for this or other problems. By taking part in this research, subjects may help themselves toward recovery and others with similar problems.

**Subject Payment.** Participants will be provided \$40 for completing the baseline screening. They will receive \$50 for attending each study visit and a \$50 bonus for completing the study/returning study equipment.

Additionally, participants will receive \$5 compensation per visit for parking and/or bus fare. As noted above, participants may earn up to \$34 across visits during the smoking relapse assessment (if achieving maximum latency and zero cigarette purchase), bringing total possible compensation to \$234/participant. Upon study completion, participants may be given the opportunity to earn an additional \$20 for referring new participants to the study that successfully enroll and also complete all study procedures.

#### **E6. Importance of the Knowledge to be Gained.**

Research participation may assist subjects in abstaining from cigarette smoking during study, and via study completion protocol, bring them into contact with treatment resources at our research center and in the community. Nicotine dependence is marked by repeated relapse, leading to devastating consequences on a personal and societal level. Currently there is no medication that has been shown to be broadly effective in improving withdrawal symptoms via improved sleep metrics. Suvorexant (and orexin agonists more broadly) may help reduce sleep disruptions and attenuate craving, helping to reduce risk of relapse. This experiment will compliment and provide valuable information to our ongoing and future addiction work, and contribute to the knowledge base in the treatment of tobacco use disorder. Our procedures have been designed to minimize the probability of risks. Our research center has an excellent track record in conducting human psychopharmacology experiments and clinical trials with the utmost attention to safety.

